- To be assigned a status of PR or CR, changes in tumor measurements must be confirmed by repeat assessments that should be performed no less than 4 weeks after the criteria for response are first met. Longer intervals as determined by the study protocol may also be appropriate.
- In the case of SD, follow-up measurements must have met the SD criteria at least once after study entry at a minimum interval (in general, not less than 6-8 weeks) that is defined in the study protocol

Duration of overall response

• The duration of overall response is measured from the time measurement criteria are met for CR or PR (whichever status is recorded first) until the first date that recurrence or PD is objectively documented, taking as reference for PD the smallest measurements recorded since the treatment started.

Duration of stable disease

• SD is measured from the start of the treatment until the criteria for disease progression are met, taking as reference the smallest measurements recorded since the treatment started.

5.3 Toxicity Assessments

To protect against and minimize potential risks, assessments of treatment-related toxicities will be performed by the study nurse every three weeks (via telephone). The NCI, Common Toxicity Criteria for Adverse Events (CTCAE, version 3.0, available at http://ctep.cancer.gov//forms/CTAEv3.pdf)), will be used as a guide to assess severity. To assess musculoskeletal adverse effects associated with EXE use, all subjects will complete modified Health Assessment Questionnaires (HAQ DI©) (Appendix A) at the start of each cycle of treatment, as previously validated [7, 17].

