Patients who are not first line will be assigned to Treatment Arm 1. Patients who are first line will be accrued to treatment Arm 2. These arms are used simply as a convenience for easier determination of the primary endpoint, and no specific accrual goals are made for each treatment arm, with a total goal of 36 subjects.

While it is assumed that reduced exposure to EXE results in fewer and less severe drugrelated toxicities, a sufficient sample size must be accrued in order to obtain a reasonable estimate of the frequency of treatment related toxicities. One benchmark will look at the incidence of joint disorders, reported by Gradishar [5], at approximately 30%. A onesided exact binomial test with a nominal 10% significance level, will have 81% power to detect a difference from a historical 30% complication rate, to a 15% complication rate with 36 subjects. Generally, however, if the PFS is equivalent to historical data, this will be considered successful, based on the assumption that reduced drug exposure will result in less toxicity. While progression free survival (time to progression or death) at 4 months (and 10 months) is calculated as a binomial (all treated patients will count and patients lost to follow-up before 4 months (10 months for first line) will count as a failure), progression-free survival will also be reported using the method of Kaplan-Meier.

6.2 Correlative Analysis

With 36 patients, correlative analysis will be exploratory in nature. No attempt will be made to adjust for multiple comparisons (except as part of standard microarray analysis) and this will be noted in any report. Changes from baseline and comparison between responders and non-responders, will be summarized. We will also do a more refined analysis of 1st line, second line and third-line patients to explore the potential impact of EXE in these different patient populations.

6.3 Reporting of results

• All patients included in this study must be assessed for response to treatment, even if there are major protocol treatment deviations or if they are later determined to be ineligible. Each patient will be assigned one of the following categories: 1) complete response, 2) partial response, 3) stable disease, 4) progressive disease, 5) early death from malignant disease, 6) early death from toxicity, 7) early death because of other cause, or 9) unknown (not assessable, insufficient data).

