7.2 Monitoring and Personnel Responsible for Monitoring

The Protocol Management Team (PMT), consisting of the PI, Collaborating Investigator, CRA/protocol nurse and statistician, is responsible for monitoring the data and safety of this study, including implementation of any stopping rules for safety and efficacy.

Data and safety will be reported to the COH DSMC using the PMT report and submitted according to the timelines in Table 1 below. Protocol specific data collection will include the following items: summary of accrual, adverse events, and treatment related mortality.

Risk Level	Phase	Standard Reporting Requirement
RL 1, RL2, and Compassionate Use Studies	No reports required	

3	I	Every 3 months from activation date, as indicated in MIDAS
3	Pilot, Feasibility, II-IV	Every 6 months from activation date, as indicated in MIDAS
4	Pilot, Feasibility, I-IV	Every 3 months from activation date, as indicated in MIDAS

.

7.3 Definitions

Adverse event (AE) - An adverse event is any untoward medical experience or change of an existing condition that occurs during or after treatment, whether or not it is considered to be related to the protocol intervention.

Unexpected Adverse Event [21 CFR 312.32 (a) – An adverse event is unexpected if it is not listed in the investigator's brochure and/or package insert; is not listed at the specificity or severity that has been observed; is not consistent with the risk information described in the protocol and/or consent; is not an expected natural progression of any underlying disease, disorder, condition, or predisposed risk factor of the research participant experiencing the adverse event.

Expected Adverse Event - Any event that does not meet the criteria for an unexpected event OR is an expected natural progression of any underlying disease, disorder, condition, or predisposed risk factor of the research participant experiencing the adverse event

Serious Adverse Event (SAE) [21 CFR 312.32] is defined as *any expected or unexpected adverse event* that results in any of the following outcomes:

- Death
- Is life-threatening experience (places the subject at immediate risk of death from the event as it occurred)
- Unplanned hospitalization (equal to or greater than 24 hours) or prolongation of existing hospitalization
- A persistent or significant disability/incapacity
- A congenital anomaly/birth defect
- Secondary Malignancy

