7.4 Reporting of Unanticipated Problems and Adverse Events

Unanticipated Problems: Most unanticipated problems must be reported to the COH DSMC and IRB **within 5 calendar days** according to definitions and guidelines at http://www.coh.org/hrpp/Pages/hrpp-policies.aspx. Any unanticipated problem that occurs during the study conduct will be reported to the DSMC and IRB by submitting electronically in iRIS (http://iris.coh.org).

Serious Adverse Events - All SAEs occurring during this study, whether observed by the physician, nurse, or reported by the patient, will be reported according to definitions and guidelines at http://www.coh.org/hrpp/Pages/hrpp-policies.aspx and Table 2 below. Those SAEs that require expedited reporting will be submitted electronically in iRIS (http://iris.coh.org/).

Adverse Events - Adverse events will be monitored by the PMT. Adverse events that do not meet the criteria of serious OR are not unanticipated problems will be reported only in the protocol continuation reports and PMT report (see Table 2 below).

Table 2: City of Hope Adverse Event and Unanticipated Problem Reporting Timelines for the DSMC and IRB

Required Reporting Timeframe to DSMC		
Attribution	UNEXPECTED	EXPECTED

Required Reporting Timelines to DSMC for AE/SAEs Investigator Initiated Studies

	Death while on active treatment or within 30 days of last day of treatment	
Possibly, Probably, Definitely Unlikely, Unrelated	5 calendar days	
	Death after 30 days of last	t active treatment/therapy
Possibly, Probably, Definitely	5 calendar days	No reporting required
Unlikely, Unrelated	No reporting required	No reporting required
	Grades 3 and 4 AND meeting the definition of "serious"	
Possibly, Probably, Definitely	5 calendar days	10 calendar days
Unlikely, Unrelated	5 calendar days	10 calendar days
	Grades 1 and 2 AND resulting in "hospitalization"	
Possibly, Probably, Definitely	5 calendar days	10 calendar days
Unlikely, Unrelated	10 calendar days	10 calendar days

Externally Sponsored Studies

Required Reporting Timeframe to DSMC		
Attribution	UNEXPECTED ¹	EXPECTED
	Death while on active treatment or within 30 days of last day of treatment	
Possibly, Probably, Definitely	No DSMC reporting required - IRB reporting may be necessary	
Unlikely, Unrelated		
	Death after 30 days of las	t active treatment/therapy
Possibly, Probably, Definitely	No DSMC reporting required - IRB reporting may be necessary	
Unlikely, Unrelated		

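### Section 5.3 limits the nurse's three-weekly call to treatment-related toxicities, which conflicts with the all-cause adverse event definition in 7.3 and may under-count joint disorders in the 6.1 comparison

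*Combined protocol and SAP*

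**What the plan says.** Section 5.3 (Toxicity Assessments) sets up the most frequent adverse event enquiry in the protocol: "assessments of treatment-related toxicities will be performed by the study nurse every three weeks (via telephone". The same section adds a musculoskeletal instrument: "all subjects will complete modified Health Assessment Questionnaires (HAQ DI©) (Appendix A) at the start of each cycle of treatment".

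Section 7.3 (Definitions) makes an untoward event an adverse event "whether or not it is considered to be related to the protocol intervention". Section 7.2 lists adverse events among the data to be collected and does not restrict them by cause. Section 7.4 says "Adverse events will be monitored by the PMT", and that events which are neither serious nor unanticipated problems "will be reported only in the protocol continuation reports and PMT report". For serious events it covers "All SAEs occurring during this study, whether observed by the physician, nurse, or reported by the patient". Its Table 2 has separate rows for events judged unlikely or unrelated.

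Section 6.1 says the sample must allow "a reasonable estimate of the frequency of treatment related toxicities". It then names the incidence of joint disorders as one benchmark, with a historical rate of about 30%. The test is a one-sided exact binomial test at a nominal 10% level, with 81% power against 15% in 36 subjects. Section 6.1 does not say whether the numerator is all joint disorders or only those judged related. It also does not say how the historical 30% was counted.

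**The concern.** Under 7.3 and Table 2, an event is recorded first and attributed afterwards. Section 5.3, read literally, reverses that order, because only toxicities already judged treatment-related fall within the call.

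Joint symptoms are where this matters most. Section 4.1.4 admits women who relapsed on an adjuvant non-steroidal aromatase inhibitor, and section 3.3 provides for patients with bone metastases. Either can be blamed for joint or bone pain. Every participant receives exemestane, so the judgement is unblinded, and the plan already expects toxicity to fall. Most joint symptoms are not serious, so the SAE route would not pick them up.

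The joint-disorder comparison is the plan's only quantified check on the assumption that less exposure means less toxicity. Section 6.1 relies on that assumption when it says that PFS merely equivalent to historical data would count as successful. An under-count would tilt that check towards confirming it.

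**Working it through.** **1. The text.** Four other parts of the protocol might make up for the wording in 5.3.
- Sections 7.2 and 7.4 have no attribution limit, but they govern events once known. They do not tell the nurse to ask about unrelated ones.
- The study calendar's compliance and toxicity row is marked only at weeks 7 and 16 of the first 18, and it refers to toxicity rather than to all adverse events.
- The forms in section 9.4 state no all-cause collection rule.
- The HAQ-DI is completed by everyone, but it scores function and pain. It does not give the number of patients with a joint disorder.

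**2. The plan's power figure.** Inputs from 6.1: n = 36, p0 = 0.30, p1 = 0.15, one-sided 10%.
- Normal approximation: Φ[(0.15 − 1.2816 × √(0.30 × 0.70/36)) / √(0.15 × 0.85/36)] = Φ[(0.15 − 0.0979)/0.0595] = Φ(0.876) = 80.9%. This matches the stated 81%. An exact test randomised to exactly 10% gives 81.1%.
- Conventional exact test: P(X ≤ 6 | 0.30) = 5.4% and P(X ≤ 7 | 0.30) = 11.2%. The second exceeds 10%, so the cut-off is 6 or fewer, with power P(X ≤ 6 | 0.15) = 71.0%.

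**3. Effect of filtering by attribution.** Two assumptions are needed, because the documents settle neither: the historical 30% is all-cause, and a share f of affected patients goes uncounted. Take a true all-cause rate of 30%, so that there is no real reduction. The counted rate is 0.30 × (1 − f), and the chance of wrongly declaring a reduction is P(X ≤ 6) with n = 36 at that rate.

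| f (assumed) | Counted rate | Chance of a false reduction |
|---|---|---|
| 0 | 0.30 | 5.4% |
| 10% | 0.27 | 11.0% |
| 20% | 0.24 | 20.5% |
| 30% | 0.21 | 34.5% |

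With the test randomised to exactly 10%, one of the versions that reproduces the plan's 81%, the same shares give 10.0%, 18.5%, 31.1% and 47.2%.

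Here f is a share of patients, not of events. A patient with several joint events still counts if any one of them is judged related.

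**The case against.** The strongest reply is that 5.3 describes one telephone call and does not say that nothing else is collected. That is right. A reader might infer that 5.3 is the only routine collection rule, so that unrelated events fall out of safety reporting. The documents do not support this: 7.2 and 7.4 collect, monitor and report adverse events without regard to cause.

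A reader might also infer that the unlikely or unrelated rows of Table 2 have no source of events. For investigator-initiated studies, the DSMC rows cover deaths, grade 3–4 events that are serious, and grade 1–2 events with hospitalization. The section 7.4 sentence on all SAEs from any observer already supplies these.

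A third tempting reading is that the joint-disorder test is biased as written. Section 6.1 does not restrict its numerator to related events, and the basis of the 30% is not given. If the 30% was itself restricted to treatment-related events, counting only those on study would be the like-for-like comparison, and an all-cause numerator would create the opposite mismatch.

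Finally, joint disorders are one benchmark, and no decision rule depends on them. All of this stands. What it leaves is the conflict between 5.3 and 7.3, and a numerator and benchmark whose attribution basis is undefined.

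**Conclusion.** The conflict is real and worth correcting, within limits. Section 5.3 applies an attribution filter, at the most frequent point of enquiry, that 7.2, 7.3 and 7.4 do not apply. Sites following it literally may fail to record non-serious joint symptoms, and these cannot reliably be recovered later.

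The statistical consequence is conditional. If the historical 30% is all-cause, losing one affected patient in ten roughly doubles the chance of a false reduction, from 5.4% to 11.0%. Losing three in ten takes it to 34.5%. The lost share is an assumption and is shown only as a range. If the 30% is treatment-related only, this bias does not arise, but the wording conflict and the undefined numerator remain. The PFS stopping and success rules and the reporting of serious events are unaffected in either case.

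**What to change.** In 5.3, replace the reference to treatment-related toxicities with all adverse events, with attribution recorded separately. In 6.1, count the joint-disorder numerator on the same attribution basis as the historical 30%, state what that basis is, and report both the all-cause and the treatment-related rates. Do not fix the numerator as all-cause before the basis of the 30% has been checked.

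The cost is protocol wording. The same calls record somewhat more events, and the reported joint-disorder rate may be slightly higher. No extra visits or patients are needed.

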5.4 Quality of Life Assessment (Appendix C)

For determination of quality of life associated with EXE use, the European Organization for Research and Treatment of Cancer (EORTC) Quality of Life Questionnaire (QLQ-C30) will be used. This instrument consists of a 30-item, cancer-specific tool which encompasses measures of physical, emotional, cognitive and social well being, in addition to measures of symptoms and overall quality of life. Questionnaires will be completed at the start of every new cycle of treatment.

5.5 Exemestane Drug Diary

To assess compliance with treatment, all patients will be supplied with a calendar of the treatment schedule at the start of each new cycle and will be instructed to track their daily consumption of EXE at home. Completed calendars will be collected at the end of each cycle of treatment.

6.0 STATISTICAL CONSIDERATIONS

6.1 Maximum Accrual: 36 Subjects

While toxicity is safely assumed to be reduced, the improvement in PFS is less clear and interim stopping conditions in case the PFS is dramatically worse than historical data [5], are incorporated in the design. The following design operating characteristics were calculated by the method of Simon, but the specific design chosen differs slightly from the Optimum or Minimax design to take into consideration the sawtooth nature of the power function [18, 19]. Patients will be defined as a "success" or "failure" based on whether they have obtained the appropriate benchmark for median PFS (see below). An interim analysis will be performed at 21 subjects. If fewer than six of the first 21 subjects are a "success", the study will be stopped for futility. If fewer than fourteen patients out of the 36 subjects are a success this will also be suggestive that this regimen does not warrant further study. This design discriminates between an encouraging "success" rate of 50% and a discouraging "success" rate of 30%. The probability of early stopping if the true success rate is 50%, is 1% whereas the probability of early stopping if the true success rate is 30%, is 36%. The overall type II error for the decision on whether or not the treatment is promising is 7%, whereas the type I error is less than 17%, when comparing a discouraging success rate of 30% to an encouraging rate of 50%.

For second or third line patients (as was done prior to the amendment to include first line patients) if patients are progression-free at the 4 month evaluation this will be considered a success. Based on recent publication (e.g. Paridaens, et al , Vol 26, No. 30, pp-4883-4890, JCO 2008) the median PFS for first line patients on EXE is approximately 10 months. As a result, we will view a "success" for first line patients if they are progression-free at 10 months.

Patients who are not first line will be assigned to Treatment Arm 1. Patients who are first line will be accrued to treatment Arm 2. These arms are used simply as a convenience for easier determination of the primary endpoint, and no specific accrual goals are made for each treatment arm, with a total goal of 36 subjects.

While it is assumed that reduced exposure to EXE results in fewer and less severe drugrelated toxicities, a sufficient sample size must be accrued in order to obtain a reasonable estimate of the frequency of treatment related toxicities. One benchmark will look at the incidence of joint disorders, reported by Gradishar [5], at approximately 30%. A onesided exact binomial test with a nominal 10% significance level, will have 81% power to detect a difference from a historical 30% complication rate, to a 15% complication rate with 36 subjects. Generally, however, if the PFS is equivalent to historical data, this will be considered successful, based on the assumption that reduced drug exposure will result in less toxicity. While progression free survival (time to progression or death) at 4 months (and 10 months) is calculated as a binomial (all treated patients will count and patients lost to follow-up before 4 months (10 months for first line) will count as a failure), progression-free survival will also be reported using the method of Kaplan-Meier.

6.2 Correlative Analysis

With 36 patients, correlative analysis will be exploratory in nature. No attempt will be made to adjust for multiple comparisons (except as part of standard microarray analysis) and this will be noted in any report. Changes from baseline and comparison between responders and non-responders, will be summarized. We will also do a more refined analysis of 1st line, second line and third-line patients to explore the potential impact of EXE in these different patient populations.

6.3 Reporting of results

• All patients included in this study must be assessed for response to treatment, even if there are major protocol treatment deviations or if they are later determined to be ineligible. Each patient will be assigned one of the following categories: 1) complete response, 2) partial response, 3) stable disease, 4) progressive disease, 5) early death from malignant disease, 6) early death from toxicity, 7) early death because of other cause, or 9) unknown (not assessable, insufficient data).

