To correlate with observations obtained in cell culture (i.e. that intermittent EXE therapy delays the time to re-growth of MCF-7aro breast cancer cells), the selected primary endpoint of this study will be progression free survival (PFS), although other clinically meaningful endpoints, such as objective response rates and clinical benefit will also be measured. That PFS correlates with acquired resistance to treatment is exemplified by prior clinical trials in which it was shown that as first line therapy, median duration of response to EXE was reported as 10 months [1]. However, as second [2] and third [3] line therapies, time to tumor progression was reported as 20.3 weeks and 2 months, respectively. In other clinical trials in which EXE was used after multiple lines of prior endocrine therapy (≥ 2), including use of prior non-steroidal AIs, time to tumor progression ranged between 14.7 weeks to 3.7 months [4,5,16]. In view of these previously reported data and in consideration of the desire to be able to complete this study in a timely manner, we have chosen to measure PFS at 4 months as a benchmark for comparison (10 months for first line patients, see statistical considerations) and as such, have incorporated eligibility criteria to reflect the patient population from which these historical data were obtained [5,16]. The rationale for inclusion of this study population was also derived in consideration of the hypothesis that after long-term estrogen deprivation of hormone receptor positive breast cancer cells in vitro, (presumed to be clinically equivalent to long-term exposure to anti-estrogens), estrogen may actually induce apoptosis [12].

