3.0 TREATMENT PLAN

3.1 Study Design

In order to test the study hypothesis that intermittent EXE may delay the time to development of acquired resistance, a pilot, phase II clinical trial will be conducted in which all study participants will receive treatment with EXE.

3.2 Treatment Dosage and Schedule

As is currently recommended, the standard approved dose of EXE is 25 mg orally per day, after a meal. Absorption of EXE is rapid, and after peak plasma levels are reached, plasma levels of EXE decline in a polyexponential manner, resulting in a terminal half life of approximately 24 hours. Given these pharmacokinetic properties and in consideration of convenience/ease of dosing, a 21-day treatment cycle, consisting of a schedule of 2 weeks on (consecutive daily dosing of 25 mg of EXE from Days 1-14), followed by 1 week off (cessation of dosing from Days 15-21), will be used.

3.3 Concurrent Treatment

Bisphosphonates

Concurrent bisphosphonates for the treatment of bone metastases will be permitted. In addition, throughout the study, concomitant medications deemed necessary for the supportive care of patients will be given at physician discretion.

Radiation

Subjects with measurable disease per RECIST criteria, who require palliative radiation to a non-target lesion, will be permitted to receive treatment without being considered as having disease progression. However, patients with measurable disease who require radiation to a target lesion will be considered as having disease progression and will be removed from study.

Subjects with non-measurable disease by RECIST criteria, who require palliative radiation to a single site, will be permitted to receive treatment and remain on study. However, subjects with non-measurable disease who required palliative radiation to more than one site will be considered as having disease progression and will be taken off study.

3.4 Number of Subjects

This trial will entail enrollment of a maximum of 36 patients for treatment, as discussed in section 6.0. The target accrual goal will be 18 subjects/year.

3.5 Treatment Duration and Follow-Up

Study subjects will remain on treatment until disease progression, the development

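### The 30% joint-disorder benchmark comes from later-line patients and has no time window, so longer treatment of first-line subjects can mask a true reduction in the pooled 36-subject test

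*Combined protocol and SAP*

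**What the plan says.** Section 6.1 introduces the toxicity comparison with "One benchmark will look at the incidence of joint disorders", which it puts at roughly 30% in the cited exemestane trial (reference 5). The method is an "exact binomial test with a nominal 10% significance level", one-sided, which "will have 81% power to detect a difference" "from a historical 30% complication rate, to a 15% complication rate with 36 subjects". No period is given over which a joint disorder must occur, and there is no adjustment for time on drug.

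The title of reference 5 describes patients who had already received a non-steroidal AI. Section 2.0 groups that trial with other later-line studies in which "time to tumor progression ranged between 14.7 weeks to 3.7 months".

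First-line patients came in by amendment. For them Section 6.1 notes that "the median PFS for first line patients on EXE is approximately 10 months" and moves the PFS success point from 4 to 10 months. First-line subjects form Arm 2 and all others Arm 1, with no accrual target for either arm. Section 3.5 begins: "Study subjects will remain on treatment until disease progression, the development"; the other reasons for stopping are toxicity, withdrawal of consent, investigator discretion and death. Section 5.3 has toxicity assessed every three weeks.

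**The concern.** The amendment accepts that a PFS benchmark from later-line patients does not suit first-line patients, and replaces it for them. The joint-disorder benchmark comes from the same kind of later-line source and was left as it was. An ever/never count grows with time at risk. A first-line subject expected to stay progression-free for about 10 months is watched, and takes drug, for longer than the patients behind the 30%. Counting both groups together against 30% is not a like-for-like comparison.

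What is at stake is how the toxicity result is read. Section 6.1 is prepared to call equivalent PFS a success because less drug is assumed to mean less toxicity. The joint-disorder test is the only formal toxicity comparison in the plan. If the pooled test shows no reduction, a reader could doubt that assumption when the cause is simply longer exposure.

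**Working it through.** **Inputs from the documents.** Null rate 30%, target 15%, n = 36, one-sided 10% and stated power 81% (Section 6.1). Later-line time to progression 14.7 weeks to 3.7 months (Section 2.0). First-line median PFS about 10 months (Section 6.1). Dosing on 14 of 21 days (Section 3.2).

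**Step 1: reproduce the 81%.** For X ~ Binomial(36, p):
- Reject at X ≤ 6: size P(X ≤ 6 | 0.30) = 5.4%, power P(X ≤ 6 | 0.15) = 71.0%.
- Reject at X ≤ 7: size 11.2%, power 83.8%.
- Randomised to exactly 10% (always reject at ≤ 6; reject at 7 with probability 0.79): power 81.1%.

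The stated 81% therefore matches the randomised exact test; a normal approximation gives 80.9%. The randomised rule is used below so that results compare directly with 81%.

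**Step 2: difference in exposure.** 14.7 weeks × 7 / 30.44 = 3.4 months. Calendar time: 10/3.7 = 2.7 to 10/3.4 = about 3.0 times longer. Drug taken: 10 × 14/21 = 6.7 drug-months, which is 1.8 to 2.0 times the 3.7 to 3.4 months on daily drug. The off-weeks do not cancel the difference.

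**Step 3: first-line incidence under three onset patterns (assumptions).** Time on drug is exponential, with rate λ = ln 2/3.7 = 0.187 per month (later line) or ln 2/10 = 0.069 (first line). The joint-disorder hazard h is the same in both lines. If risk lasts as long as treatment, incidence = h/(h + λ). If risk is confined to the first W months, incidence = [h/(h + λ)] × [1 − exp(−(h + λ)W)]. In each case h is set so that later-line incidence is 15%, the plan's target. For the constant hazard:
- h = (0.15/0.85) × 0.187 = 0.033 per month
- first-line incidence = 0.033/(0.033 + 0.069) = 32.3%

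The same calculation with W = 6 gives 20.1%, and with W = 3 gives 17.6%.

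**Step 4: power of the pooled test**, from the distribution of the total count when k of 36 subjects are first line:

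| First line, k | Risk in first 3 months | Risk in first 6 months | Constant hazard |
|---|---|---|---|
| 0 | 81% | 81% | 81% |
| 6 | 79% | 77% | 66% |
| 12 | 77% | 72% | 48% |
| 18 | 75% | 68% | 32% |
| 24 | 72% | 63% | 20% |

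With the plain cut-off of 6 or fewer, the fall at k = 18 is from 71% to 63%, 55% or 21%.

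**Step 5: direction.** Now set h so that later-line incidence is 30%, meaning no true reduction. At k = 18 the chance of declaring one falls from 10% to 5.6%, 3.1% or 0.3%. Longer exposure makes a false claim of lower toxicity less likely.

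**Step 6: power if only Arm 1 is tested** (30% v 15%, same randomised basis): 75% with n = 30, 68% with n = 24, 57% with n = 18.

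**The case against.** The strongest reply is that this test decides nothing. Section 6.1 offers it as one benchmark, alongside the aim of estimating toxicity frequency reasonably well. Whether the regimen merits further study rests on PFS counts alone (at least 6 of 21, then at least 14 of 36). That stands, and it limits the concern to interpretation of the toxicity result.

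Second, the constant-hazard case is extreme. It implies that first-line patients on daily drug would reach 0.0803/(0.0803 + 0.0693) = 54%, where 0.0803 = (0.30/0.70) × 0.187. Nothing in the documents supports such a rate: Section 8.2 lists arthralgia at 14.6–28.8% across adjuvant and metastatic use, although that is a different term with no durations given. A reader might infer from this case that the pooled test is close to useless. The documents do not support that, because they give neither onset timing nor the first-line share, and with early onset the loss is modest.

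Third, a reader might conclude that the test should simply be confined to Arm 1. That does not follow either. With 18 first-line subjects the Arm 1 test has 57% power, below the pooled 75% or 68% under early onset; it is better only when the hazard is near constant (32%). Arm 1 also differs from the benchmark population, since Sections 4.1.4–4.1.5 do not require a prior non-steroidal AI.

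Finally, Section 6.2 plans an exploratory look by line of therapy. It does not name joint disorders and leaves the pooled comparison with 30% unqualified, so it only partly answers the point.

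**Conclusion.** The point holds as a matter of comparability. The amendment made the PFS benchmark line-specific and left the joint-disorder benchmark pooled, without a time window, so longer time at risk in first-line subjects can mask a true reduction. The effect is conservative and bears on a secondary benchmark, not on the PFS decision rule. With half the subjects first line, power for 30% v 15% drops from 81% to about 75%, 68% or 32%, depending on onset; the last is the upper bound of the patterns examined.

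These figures assume exponential time on drug, a 3.7-month later-line median, and the same hazard in both lines. Time on treatment is inferred from PFS, because the documents give no treatment durations. Section 2.0 does not say which progression figure belongs to reference 5, and the observation period behind the 30% is not stated. It would go too far to say that the trial's conclusion is at risk, or that toxicity could be wrongly declared lower through this route.

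**What to change.** - Report joint-disorder incidence separately for Arm 1 and Arm 2, each with an exact confidence interval and a summary of time on treatment.
- Set only the Arm 1 estimate beside the 30%, described as the closer match and not an identical one.
- Add incidence within a common early window for both arms, for example the first 4 months (an assumption). Under the exponential model, mean time at risk within 4 months is (1 − e^(−0.187×4))/0.187 = 2.8 months in later-line and (1 − e^(−0.069×4))/0.069 = 3.5 months in first-line subjects. The ratio drops from 2.7 to about 1.2. The documents give no historical rate for this window, so it serves to compare the arms.
- Give events per patient-month as description only, since that rate assumes a constant hazard and would dilute the first-line figure if onset is early.
- If the pooled test is kept, state that it is biased against showing a reduction as the first-line share rises, that the 81% assumes the 30% rate applies to every subject, and which cut-off will be used.

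The cost is analysis wording and one table. Arms are already assigned by line, and treatment forms, drug diaries and three-weekly toxicity assessments are already planned. The downside is lower precision in Arm 1: power of about 75%, 68% or 57% with 30, 24 or 18 subjects, on the same basis as the 81%.
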